### **5.3.4. Missing Pharmacokinetic (PK) Data**

In all data presentations (except listings), concentrations below the limit of quantification (BLQ) will be set to zero. (In listings BLQ values will be reported as “<LLQ”, where LLQ

will be replaced with the value for the lower limit of quantification.) If a summary statistic is a BLQ value, it will also be reported as zero.

In summary tables and plots of median profiles, concentrations will be set to missing if one of the following cases is true:

- A concentration has been reported as ND (i.e., not done) or NS (i.e., no sample);
- A deviation in sampling time is of sufficient concern or a concentration has been flagged as anomalous by the clinical pharmacologist.

Summary statistics will not be presented at a particular timepoint if more than 50% of the data are missing. Actual PK sampling times will be used in the derivation of PK parameters.

If a PK parameter cannot be derived from the concentration data, the parameter will be coded as NC (i.e. not calculated). NC values will not be generated beyond the day that a patient discontinues.

In summary tables of PK parameters, statistics will be calculated by setting NC values to missing; and statistics will not be presented if more than 50% of the data are NC and statistics will be presented for  $\geq 3$  evaluable measurements .

If an individual patient has a known biased estimate of a PK parameter, this will be footnoted in summary tables and will not be included in the calculation of summary statistics.

### **5.3.5. Missing ECG Data**

For ECG parameters, no values will be imputed for missing replicates within a scheduled assessment. Thus if the three triplicate measurements for an ECG parameter are not available, then the average will not be computed.

## **6. ANALYSES AND SUMMARIES**

If both adult and pediatric patients enrollment are completed and respective LPLV are included in the same same database release, all summary tables will have separate tabulations (columns) for adult and pediatric patients, and also a total column combining adult and pediatric patients, unless noted otherwise. If adult and pediatric patients are to be reported at different times, for example if adult LPLV is reached while pediatric enrollment is still ongoing, with pediatric patients summary to be reported at a later database release then summary tables may not contain a total column.

Listings will be provided as required for an ICH CSR. Additional details for some data listings are described for some data types in the following sections. As relevant, listings or summary tables focused on COVID-19 will be provided such as participants affected by COVID-19 related study disruption, protocol deviations, COVID-19 related deaths, COVID-19 related discontinuations.

## 6.1. Primary Endpoint

### 6.1.1. Change in QTcF from baseline

ECG measurements from the ECG core laboratory (an average of the triplicate measurements) will be used for the statistical analysis and all data presentations. Only the scheduled ECGs from adult patients in Cycle 1 and the particular timepoints of Day 4, 0 hours, and Day 7 at 0, 2, 4, and 6 hours will be interpreted for the primary analysis. The last available planned triplicate measurements prior to first dose will be used as baseline.

QT measurements will be corrected by heart rate (QTc) according to Fridericia's (QTcF) method.

A linear model (for adult patients and pediatric patients separately) with the Cycle 1 nominal timepoints as a fixed effect and unstructured variance/covariance to account for the repeated measurements from patients will be used for the primary analysis to estimate the mean change in QTcF (primary endpoint) at the post baseline nominal timepoints for Cycle 1 along with the estimated least squares means and 2-sided 90% confidence interval for the mean. Confidence intervals will use the approximate t distribution with degrees of freedom by Kenward Rogers method. Refer to Section 5.2.8 for further details of derivations. Although the 90% CI for the mean change in QTcF from the Cycle 1 Day 4, 0 hours, and Cycle 1 Day 7, at 0, 2, 4 and 6 hours summarized for adult patients will be interpreted (see Section 5.1), all Cycle 1 timepoints will be included in the estimation.

Summary will be for the QTc analysis set. The least squares mean and its 90 % confidence interval will be displayed graphically.

Additional summaries of QT interval data are described in Section 6.6.5 along with the summary of other ECG data.

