### 5.1. Hypotheses and Decision Rules

The primary QTc analysis will be based on a non-inferiority hypothesis testing framework. If the upper bounds of one-sided 95% confidence intervals of change from baseline in QT measurements using Fridericia's heart rate correction for adult patients for each of the QTc

sampling time points (Day 4, 0 hours, and Day 7, at 0, 2, 4 and 6 hours) from Cycle 1 are below 20 msec, the post dose QTc interval will be considered to be “non-inferior” to the baseline; the QTc effect of GO will be concluded to be not unacceptable.

Thus with an overall 1-sided significance level of 0.05 and a non-inferiority margin of 20 msec, assuming a standard deviation of 18.8 msec and a mean change from baseline for QTcF up to 10 msec, 50 adult patients will provide 90 % power for assessing the 5 QTc sampling timepoints using paired difference in means with the t distribution. **CCI**

The inclusion of 6 additional pediatric patients ( $12 \leq \text{age} \leq 17$  years) was determined based on agreement with CHMP.

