### **5.2.8. ECG Derivation Details**

#### **5.2.8.1. Corrected QT interval derivation**

$$\text{Fridericia's heart rate correction: } \frac{QT}{\sqrt[3]{60/HeartRate}}$$

$$\text{Bazzett's heart rate correction: } \frac{QT}{\sqrt{60/HeartRate}}$$

The ECG core laboratory (vendor) will provide the corrected QT intervals according to the Fridericia’s and Bazzett’s corrections.

A study specific correction for adult patients will be derived as  $QT/(RR)^S$  where S is determined as follows:

The study specific QT correction factor (ICH E14 Step 4, May 12, 2005) will be derived for adult patients in the QTc analysis set using the individual replicates from the selected baseline (baseline is defined in Section 3.4) QT and RR.

No study specific QT correction factor will be assessed for the 6 pediatric patients.

Prior to estimating the regression, QT and RR will be transformed by the natural logarithm to  $\ln(QT)$  and  $\ln(RR)$ , respectively.  $\ln(RR)$  will be treated in the regression as the explanatory variable with  $\ln(QT)$  as the response variable. The regression equation will be as follows:

$$\ln(QT) = \text{Intercept} + S \times \ln(RR) + \text{Error}$$

Where S = slope of the regression line.

Once (S) is estimated, it will be used to derive the study specific QT correction, QTcS, for adult patients in the QTc analysis set.

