#### **5.2.8.3. Change from baseline**

The change from baseline calculations for ECG parameter measurements is derived from the triplicate averaged measurements. Change from baseline is defined as a patient's parameter value at a particular timepoint minus baseline value (value - baseline value). Change from baseline calculations should only use post-dose ECG measurements at the scheduled nominal timepoints (Day 1 at 1, 2, 4 hours; Day 4 at 0, 2 hours; Day 7 at 0, 2, 4, 6 for Cycle 1; and in Cycle 2 Day 1 at 0, 2 hours; Day 7 at 0, 2 6 hours). Baseline is defined in Section 3.4.

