#### **6.6.5.3. Change from baseline**

The change in QTc (QTcF, QTcB and/or QTcS) from baseline will be summarized using descriptive statistics (n, mean, median, standard deviation (SD), minimum, maximum for each cycle and nominal time point within cycle.

A linear model (for adult patients and pediatric patients separately) with the Cycle 1 nominal timepoints as a fixed effect and unstructured variance/covariance to account for the repeated measurements from patients will be used to estimate the mean change from baseline (in QTcB and/or QTcS) at the post baseline nominal timepoints for Cycle 1 along with the estimated least squares means and 2-sided 90% confidence interval for the mean.

Confidence intervals will use the approximate t distribution with degrees of freedom by Kenward Rogers method.

In addition to QTc, the change from baseline in ECG parameters of HR, PR interval, QRS interval, QT interval will be summarized similarly with descriptive statistics (n, mean, median, standard deviation (SD), minimum, maximum).

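### The unstructured covariance model planned separately for 6 pediatric patients over 9 Cycle 1 time points cannot be estimated, so the pediatric model-based 90% intervals cannot be produced as written

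*SAP*

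**What the plan says.** SAP 6.1.1 defines the model for the change in QTcF as "A linear model (for adult patients and pediatric patients separately) with the Cycle 1 nominal timepoints as a fixed effect and unstructured variance/covariance". It gives 90% intervals for the least squares means with Kenward-Roger degrees of freedom. Only five adult time points are interpreted, but "all Cycle 1 timepoints will be included in the estimation".

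SAP 5.2.8.3 lists the post-dose times: "Day 1 at 1, 2, 4 hours; Day 4 at 0, 2 hours; Day 7 at 0, 2, 4, 6 for Cycle 1". SAP 5.1 gives the size of the second group: "The inclusion of 6 additional pediatric patients".

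The same model appears in two other places. SAP 5.2.11 states it without limiting it to adults. SAP 6.6.5.3 says it "will be used to estimate the mean change from baseline (in QTcB and/or QTcS"), for adults and children separately. For children this means QTcB only, because SAP 5.2.8.1 states: "No study specific QT correction factor will be assessed for the 6 pediatric patients".

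The SAP gives no simpler covariance structure and no rule for non-convergence of this model. Protocol 9.3.1 describes a different model, with patient as a random effect.

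**The concern.** An unstructured covariance needs enough patients to estimate every variance and covariance among the time points. Six patients cannot supply that for nine time points. If so, the specified pediatric analysis has no solution, and any interval that software prints would reflect its stopping rule and not the data.

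What is at stake is the only interval the SAP plans for the pediatric change in QTcF. The t-based interval in SAP 6.6.5.2 is for absolute values, and the descriptive summary of change in SAP 6.6.5.3 has no interval. Without a prespecified replacement, the method could end up being chosen once the pediatric data are in hand.

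**Working it through.** **Inputs.** Children: 6 (SAP 5.1). Post-dose Cycle 1 time points: 3 + 2 + 4 = 9 (SAP 5.2.8.3), all in the fit (SAP 6.1.1). Adults: 50, with SD 18.8 msec, mean change 10 msec, margin 20 msec and one-sided 0.05 (SAP 5.1). REML is inferred from the Kenward-Roger wording; ML is checked as well.

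**1. The plan's own figure.** The only operating figure is the adult power of 90%. The noncentrality is 10 / (18.8/√50) = 3.76. Power at one time point is 0.9805, and 0.9805^5 = 0.906. The stated 90% is reproduced. The documents give no corresponding figure for children.

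**2. Dimension.** The covariance has 9 × 10 / 2 = 45 parameters. With 9 means that is 54 parameters, against at most 6 × 9 = 54 observations.

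**3. Rank.** After the time-point means are removed, the residual cross-product matrix S has rank at most n − 1. For 6 children that is 5, so 9 − 5 = 4 directions show no residual variation. Rank is 8 at n = 9 and first reaches 9 at n = 10.

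**4. Likelihood.** Apart from constants, −2 log-likelihood is m·log|Σ| + tr(Σ⁻¹S), with m = n − 1 for REML and m = n for ML. Let the variance in the 4 empty directions be ε. They add nothing to the trace and 4·m·ln ε to the first term. Each 100-fold cut in ε therefore lowers −2 log-likelihood by:

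- REML: 5 × 4 × ln 100 = 20 × 4.605 = 92.1
- ML: 6 × 4 × ln 100 = 24 × 4.605 = 110.5

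Log-likelihood on simulated data (SD 18.8, assumed correlation 0.5):

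| ε | n = 6, REML | n = 6, ML | n = 10, REML |
|---|---|---|---|
| 100 | −127.8 | −150.8 | −198.8 |
| 1 | −81.7 | −95.5 | −198.8 |
| 0.0001 | 10.4 | 15.0 | −198.8 |
| 0.00000001 | 102.5 | 125.5 | −198.8 |

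At n = 6 the log-likelihood rises without limit. At n = 10 no direction is empty, so ε plays no part and the maximum is finite. Direct REML optimisation agrees. At n = 6, −2 log-likelihood kept falling (229.7, 220.6, 205.8, 199.6) as the smallest eigenvalue fell to about 1e-6. With 10% of values missing it also kept falling, from 222.7 to 191.6. At n = 50 it settled at 2848.83 with smallest eigenvalue 80.6, so the adult model is estimable.

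**5. Point estimates.** In a model with time as the only fixed effect, a time point observed in every child has a least squares mean equal to its arithmetic mean, whatever the covariance. Only time points with a missing value depend on the covariance. Such gaps are plausible, since "if the three triplicate measurements for an ECG parameter are not available, then the average will not be computed". The documents give no missing rate. If 2%, 5% or 10% is assumed, the chance of at least one gap is 1 − (1 − q)^54 = 66%, 94% or 99.7% when the 54 triplicates are lost independently. It is 1 − (1 − q)^18 = 30%, 60% or 85% when whole dosing-day visits (6 × 3 = 18) are lost.

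**6. Replacement interval.** Half-width = t(0.95, n − 1) × SD / √n, with the adult SD of 18.8 assumed for children:

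- n = 6: 2.015 × 18.8 / 2.449 = 15.5 msec
- n = 5: 2.132 × 18.8 / 2.236 = 17.9 msec
- n = 4: 2.353 × 18.8 / 2 = 22.1 msec

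**The case against.** The strongest reply is that little is lost. Children have no hypothesis, margin or decision rule; SAP 5.1 states the criterion using "Fridericia's heart rate correction for adult patients for each of the QTc" sampling time points. SAP 6.6.5.3 already reports pediatric n, mean and SD of the change at each time point, and a reader can compute a t interval from those three numbers. This stands, and it sets the importance at minor. It does not make the specified model estimable.

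A second reply is that only five time points matter. With five in the fit, 6 complete children would just reach full rank (5 of 5). But SAP 6.1.1 puts all Cycle 1 time points into the estimation.

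A third is that the gap could still be closed in time. SAP Table 1 records that pediatric enrollment was not complete at version 2, and SAP 5 and 5.2 allow a later pediatric release. The failure follows from 6 and 9 alone and needs no data. A reader might infer that a replacement must be picked after the pediatric results are seen; the documents do not support that. Protocol 9.3.1 also contains a model that can be fitted, although the SAP does not name it as a fallback.

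**Conclusion.** The pediatric model in SAP 6.1.1, repeated in SAP 5.2.11 and in SAP 6.6.5.3 for QTcB, cannot be fitted with 6 children. Its 90% intervals cannot be obtained as written, and no alternative is specified. This rests only on the planned 6 patients, the 9 listed time points and the unstructured covariance. Protocol 6.3 allows replacement of patients who withdraw, but nothing in the documents plans for the 10 or more complete children that would be needed.

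Two stronger readings should be resisted. One is that the primary conclusion is at risk: it is not, because adults are modelled separately and only adult results enter the decision. The other is that no pediatric estimates survive, or that one missing value removes all of them. Time points observed in every child keep their arithmetic means; only the incomplete ones cannot be obtained from the model.

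The half-widths also assume that the adult SD of 18.8 msec holds in children, which the documents do not say. Importance: minor.

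**What to change.** Before pediatric database release, amend SAP 5.2.11, 6.1.1 and 6.6.5.3 together, so that the sections do not contradict each other:

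- Restrict the unstructured model to adults, otherwise unchanged.
- For children, report the mean change at each time point (QTcF, and QTcB in 6.6.5.3) with a t-based 90% interval from the SD observed at that time point. SAP 6.6.5.2 already uses this method for absolute QTc.
- Show these means and intervals in the pediatric version of the figure planned in SAP 6.1.1.

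The cost is SAP wording and a few lines of code, with no new data. The downside is width, because each interval uses only the data at its own time point. At SD 18.8 and n = 6 the half-width is 15.5 msec. The Protocol 9.3.1 random-patient model would give about 13.1 to 14.0 msec at assumed correlations of 0.3 to 0.7, but it assumes equal variances and equal correlations across time points. If the change is made only after release, SAP section 2 requires it to be described in the study report as a deviation.

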## 6.2. Secondary Endpoints

### 6.2.1. Pharmacokinetic Endpoints

#### 6.2.1.1. Non-Compartmental Analysis

To assess the pharmacokinetics of GO (represented by total hP67.6 antibody, conjugated calicheamicin, and unconjugated calicheamicin if possible), the PK parameters detailed in Section 3.2.1 will be summarized for subjects in the PK analysis set (as defined in Section 4.4.2). Missing values will be handled as detailed in Section 5.3.4.

Each PK parameter for each analyte (total hP67.6 antibody, conjugated calicheamicin, and unconjugated calicheamicin) will be summarized using the set of descriptive statistics as specified in the table below:

**Table 2. PK Parameters to be Summarized Descriptively**

Parameter	Summary Statistics
AUC last , AUC 0-72 , AUC 0-336 , AUC infa , C max , CL *,a and V ss *,a	N, arithmetic mean, median, cv%, standard deviation, minimum, maximum, geometric mean and geometric cv%.
T max	N, median, minimum, maximum.
t 1/2a	N, arithmetic mean, median, cv%, standard deviation, minimum, maximum.

\*for total hP67.6 antibody onlya if data permit

Supporting data from the estimation of t1/2 and AUCinf will be listed by analyte or provided in data sets where applicable: terminal phase rate constant (kel); goodness of fit statistic from the log-linear regression (r); the percent of AUCinf based on extrapolation (AUCextrap%); the first, last, and number of time points used in the estimation of kel.

Presentations for plasma concentrations of GO (total hP67.6 antibody, conjugated calicheamicin, and unconjugated calicheamicin) will include:

- Listings will be consistent with ICH CSR requirements and may include: A listing of all concentrations sorted by participant ID, cycle, day and nominal time postdose. The concentration listing will also include the actual times. Deviations from the nominal time will be given in a separate listing.
- A summary of concentrations by nominal time postdose, where the set of descriptive statistics will include n, mean, median, standard deviation, coefficient of variation(cv), minimum, maximum and the number of concentrations above the lower limit of quantification.
- Median concentrations time plots (on both linear and semi-log scales) against nominal time postdose for Cycle 1 Day 1 and Cycle 1 Day 7 .

For summary statistics, median plots by sampling time, the nominal PK sampling time will be used, for individual participant plots by time, the actual PK sampling time will be used.

#### 6.2.1.2. Population Pharmacokinetics/Pharmacodynamics

Population PK/PD modeling analyses will be explored, as necessary, based on emerging safety/clinical response data. The results of these population modeling analyses will be reported separately from the clinical study report.

#### 6.2.2. Immunogenicity

Immunogenicity will be summarized for the immunogenicity analysis set (as defined in Section 4.4.4).

The percentage of patients with positive ADA and NAb will be summarized (eg. at baseline, treatment-induced (positive for the first time after dosing), and treatment-boosted (pre-existing positive titers that were at a higher level post-baseline), and overall (treatment-induced + treatment-boosted). The overall percentage will be computed excluding baseline positive patients without any post-dose assessment. The other percentages will be based on the number of patients in the immunogenicity analysis set.

For patients with positive ADA/NAb, the magnitude of the titer will be described with summary statistics (median, Q1, Q3) for positive baseline titers, peak titer for treatment-induced and treatment-boosted, and titer fold increase for treatment-boosted (calculated as the ratio of peak post-dose titer to baseline titer), if data permit.

For patients with treatment induced ADA/NAb, time of onset, and duration will also be described with summary statistics (median, Q1, Q3), if data permit. Onset of ADA/NAb will be calculated as date of first positive result – date of first dose +1. Duration of ADA/NAb will be calculated as date of last positive result – date of first positive result +1. The number and percent of transient and persistent positive ADA/NAb will be summarized out of the number of patients with treatment-induced ADA/NAb.

Transient ADA/NAb will be defined as treatment-induced ADA/NAb meeting the following conditions:

- detected only at one sampling time point during the treatment or follow-up (excluding the last sampling time point which will be considered persistent unless shown to be undetectable at a later time) or
- detected at two or more sampling time points during the treatment (including follow-up), where the first and last positive samples (irrespective of any negative samples in between) are separated by a period less than 16 weeks, and the last sampling time point is negative

Persistent ADA/Nab will be defined as treatment-induced ADA/NAb meeting the following conditions:

- detected at two or more sampling time points during the treatment (including follow-up), where the first and last positive samples (irrespective of any negative samples in between) are separated by a period of 16 weeks or longer or
- detected only in the last treatment sampling time point or at a sampling time point with less than 16 weeks before a negative last sample.

Analyses to assess the impact of ADA on safety are described in Section 6.6.1. The impact of ADA on PK will be assessed in population PK analysis and will be reported separately.

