6.2.4. The End-of-Treatment (EOT) Visit (36 Days after the Last Dose of GO)

- This visit is required for all patients. It occurs 36 days after the last dose of GO. However, in the event that a patient requires initiation of a consolidation treatment or another anti-cancer therapy, the end-of-treatment visit, including procedures (laboratory tests, PE, sampling for PK and ADA/NAb assays), should be performed before the initiation of a consolidation treatment or subsequent anti-cancer therapy. Adverse events, safety laboratory tests, and associated concomitant medications must continue to be collected in the CRF through at least 36 days after the last dose of GO or start of subsequent therapy, eg, consolidation and/or conditioning regimen, whichever occurs first.
- Adverse Event (AE) Assessments should be documented and recorded at each visit using NCI CTCAE version 4.03 up to EOT visit, or start of subsequent anticancer therapy, eg, consolidation and/or conditioning regimen, whichever occurs first.
- Concomitant medications and treatments will be recorded up to 36 days after the last dose of study treatment or starting subsequent anticancer therapy (eg, consolidation or conditioning regimen).
- EOT visit procedures and tests include the following:
 - Blood sample collection for PK assessment and ADA/NAb measurement;
 - Limited physical examination, with clinical judgment to evaluate potential areas of AML relapse and any clinically significant abnormalities which may include the following body systems: general appearance, skin, head/eyes/ears/nose/throat, heart, lungs, testes, abdomen, extremities, neurological, back/spinal, and lymph nodes; including worsening of medical history conditions;

- Laboratory evaluations, including pregnancy test, according to the [Schedule of Activities \(Table 1\)](#).
- Disease assessment for final determination of remission status should be conducted no later than 36 days after last dose of GO (EOT) or/and prior to the start of subsequent anticancer therapy (eg, consolidation and/or conditioning regimen).

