## 4.4. Other Analysis Sets

### 4.4.1. QTc Analysis Set

The QTc analysis set will include patients in the safety analysis set who have a baseline ECG and at least one post-dose ECG.

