### 4.4.4. Immunogenecity Analysis Set

The immunogenicity analysis set include patients in the safety analysis set who have at least 1 immunogenicity sample with results.

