#### 5.2.10. Analyses for Binary Data

Binary variables will be summarized by frequency counts and percentages. Unless otherwise specified, the calculation of proportions will include the missing category. Therefore counts of missing observations will be included in the denominator and presented as a separate category.

If the analysis refers only to certain cycle or timepoints, then percentages will be based on the number of patients with an assessment at that cycle or timepoint, unless otherwise specified.

Best response will be summarized as a binary variable using frequency counts, percentages, and will additionally include a 95% Clopper-Pearson CI for the rate.

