#### **6.6.2. Deaths**

The frequency (number and percentage) of patients in the safety analysis set who died and who died within 36 days after last dose of study treatment as well as the cause of death, will be tabulated based on information from the 'Notice of Death' CRFs.

The frequency (number and percentage) of patients in the safety analysis set who died within 30 days of first dose of study treatment will also be provided.

Date and cause of death will be provided in individual patient data listing (as needed to be compliant with ICH required listings) together with selected GO dosing information (date of first / last administration).

Refer to Section 6.2.4 for the description of the summaries of all deaths observed in the study.

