Several laboratory tests have bi-directional grading criteria defined so that both low (hypo) and high (hyper) values will be graded separately. Each criterion will be summarized separately. In the cases where a value is graded as a Grade 1, 2, 3, or 4 for one of the directions, that value will also be assigned as a Grade 0 for the opposite direction for that test. For example, a value meeting the criteria for Grade 3 Hypercalcemia will be classified as a Grade 0 Hypocalcemia.

The following summaries will be provided for the safety analysis set.

The denominator for percentages will be the number of patients treated in the group being summarized with at least 1 post baseline assessment of the laboratory parameter.

Displays will be organized by laboratory category: Hematology parameters including coagulation parameters will be summarized together, chemistry parameters will be summarized together, and urinalysis parameters will be summarized together. Laboratory parameters with CTCAE grades will be summarized separately from laboratory parameters with no CTCAE grades.

For each CTCAE term, patients will be counted according to the worst (maximum) CTCAE grade on treatment (excluding baseline values). Baseline is defined in Section 3.4. If there are multiple assessments that meet the baseline definition on the same day without the ability

to determine which was truly last, then the worst CTC grade will be assigned as the baseline CTC grade.

The following summary tables will be created:

- Shift summary of laboratory parameters of baseline CTCAE grade by maximum post baseline CTCAE grade.
- Shift summary of laboratory parameters from  $\leq$  Grade 2 at baseline to  $\geq$  Grade 3 post-baseline.

The non-CTC graded laboratory tests (red blood cells, hematocrit, BUN, LDH) along with urinalysis test (pH) will be presented according to the following categories overall: below normal limit, within normal limits, and above normal limits. In the unlikely event that for a given participant, clinically significant abnormalities are noted in both directions (eg,  $>$  ULN and  $<$  LLN), then both abnormalities are counted. The remaining urinalysis tests (albumin, glucose, blood/hemoglobin, ketones/acetone) will be categorized as negative or positive.

A shift summary of laboratory test results with no CTCAE criteria of baseline assessment by worst on-treatment assessment will be created. .

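### ADA/NAb summaries: baseline-negative patients never tested after dosing dilute the incidence, and the transient and persistent classes overlap and leave gaps

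*SAP*

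**What the plan says.** **Denominators.** SAP 4.4.4 admits to the immunogenicity analysis set any safety-set patient "who have at least 1 immunogenicity sample with results". The Cycle 1 Day 1 pre-dose sample (Protocol 6.2.2.1) satisfies this on its own. For the overall rate, defined as induced plus boosted, SAP 6.2.2 states: "The overall percentage will be computed excluding baseline positive patients without any post-dose assessment". For the baseline, induced and boosted rates: "The other percentages will be based on the number of patients in the immunogenicity analysis set". Protocol 9.3.2.5 names the safety set instead, which requires no post-dose sample either.

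**Duration classes.** In SAP 6.2.2, both classes are reported as a share of treatment-induced patients.

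- Transient: positive at one time point that is not the last; or at several points spanning under 16 weeks with a negative last sample.
- Persistent: positives spanning 16 weeks or more; or positive only at the last point, or at a point under 16 weeks before a negative last sample.

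No precedence rule is given.

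**Sampling.** Post-dose ADA samples fall on Days 15 and 21 of each cycle (Protocol 6.2.2.4, 6.2.3.4) and at the end-of-treatment (EOT) visit, 36 days after the last dose. Sampling continues after EOT only for patients who are ADA positive at EOT (Protocol Table 2 footnote m, and 6.2.5).

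**The concern.** A patient who is baseline negative and never tested after dosing cannot be treatment-induced (no post-dose result) or treatment-boosted (not positive at baseline), yet counts in the denominator of both rates and of the overall rate. In effect the patient is scored negative. The overall rule already accepts that untestable patients should be dropped, but applies this only to the baseline-positive ones. The SAP is stricter elsewhere: laboratory percentages use patients "with at least 1 post baseline assessment of the laboratory parameter" (6.6.3), and the QTc set needs patients "who have a baseline ECG and at least one post-dose ECG" (4.4.1).

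With the duration classes, one patient can be counted twice or not at all. The two percentages can then add to more or less than 100%, and two programmers can report different splits from the same data.

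ADA/NAb incidence is a named secondary endpoint, and the protocol lists anti-drug antibodies among the post-marketing-requirement topics. Few positives may be seen, so one misplaced patient would be visible in the table.

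**Working it through.** The documents state no ADA rate or ADA sample size, so there is no figure to reproduce.

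**1. Denominator.** Let N be the immunogenicity set, x the treatment-emergent positives and k the baseline-negative patients with no post-dose result. With no other untested patients, the overall rate as written is x/N; among tested patients it is x/(N − k). N = 50 is the planned adult number. The values x = 4 and k = 1 to 5 are assumptions.

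| k | As written | Tested only |
|---|---|---|
| 1 | 4/50 = 8.0% | 4/49 = 8.2% |
| 3 | 4/50 = 8.0% | 4/47 = 8.5% |
| 5 | 4/50 = 8.0% | 4/45 = 8.9% |

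- The exact (Clopper-Pearson) 95% interval for 4/50 is 2.2% to 19.2%.
- Relative understatement at k = 5: 1 − (4/50)/(4/45) = 10.0%, which equals the untested share 5/50.
- For the overall row this equality holds when no untested patient is baseline positive. If 1 of the 5 untested is, the rule already removes that patient: 4/49 = 8.2% against 4/45 = 8.9%, a relative understatement of 8.2%.
- With no positives at all, the upper 95% limit is 7.1% for n = 50 and 7.9% for n = 45.

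**2. Overlap.** The persistent limit is 16 × 7 = 112 days. For a patient who is negative at EOT, EOT is the last planned sample. The longest gap is from Day 15 to EOT.

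- One cycle, nominal: EOT on Day 7 + 36 = 43; gap 43 − 15 = 28 days (4.0 weeks).
- One cycle, longest: Protocol Table 3 allows delays of up to 2 days between infusions. Taken twice, the third dose falls on Day 11 and EOT on Day 47. With the visit windows (EOT +2, Day 15 −1): 49 − 14 = 35 days (5.0 weeks).
- Two cycles, latest nominal: Cycle 2 starts on Day 7 + 42 = 49; EOT on 49 + 6 + 36 = Day 91; gap 91 − 15 = 76 days (10.9 weeks).
- Two cycles, longest: Cycle 2 starts on Day 11 + 42 = 53; last dose on 53 + 6 + 4 = Day 63; EOT on Day 99, or 101 with its window; gap 101 − 14 = 87 days (12.4 weeks).

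All gaps are below 112 days. Every single positive before EOT that has cleared by EOT therefore meets both definitions.

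**3. All seven one-cycle patterns (Day 15, Day 21, EOT as last sample).**

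| Pattern | Class under SAP 6.2.2 |
|---|---|
| + − − | both |
| − + − | both |
| + + − | transient; also persistent if the restriction to a sole detection is not carried into the second half of that condition |
| − − + | persistent |
| + − + | neither |
| − + + | neither |
| + + + | neither |

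The last three fail transient because the last sample is positive. They fail persistent because the positives span at most 28 days (35 with delays and windows) and no negative last sample follows. The two-cycle schedule behaves the same way: all four single positives before EOT meet both definitions, and all four two-positive patterns ending in a positive EOT meet neither (largest nominal span 76 days).

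**4. Effect on the split.** Assume 4 induced patients, 2 with a single early positive cleared by EOT and 2 clearly persistent. As written, transient is 2/4 = 50% and persistent 4/4 = 100%, summing to 150%. An exclusive rule gives 50%/50% or 0%/100%, depending on precedence.

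**The case against.** The denominator effect is small even under the assumptions above. To be untested, a patient must miss Day 15, Day 21 and EOT. Protocol 6.2.4 also brings EOT forward: its procedures "should be performed before the initiation of a consolidation treatment or subsequent anti-cancer therapy". Early death is the obvious route, and SAP 6.6.2 tabulates patients "who died within 30 days of first dose of study treatment", but those who die after about Day 15 may already have a sample. All of this stands.

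It can also be said that the SAP's general rule is to keep missing results: "counts of missing observations will be included in the denominator and presented as a separate category" (5.2.10). If that rule is applied here, a reader could recompute the rate. This stands in part: the untested count may be visible, but the printed percentage stays diluted.

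Keeping unassessed patients in a denominator is not foreign to this SAP either. Patients without a documented response are non-responders (3.2.3), and adverse-event rates use all treated patients (6.6.1). The parallel is weak. Counting the unassessed as non-responders is cautious for efficacy; counting the untested as antibody negative leans toward the favourable result.

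Three stronger readings are tempting, and the documents do not support them.

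- **A 20% understatement.** With 5 untested baseline-negative and 5 tested baseline-positive patients, induced could be read as 4/50 = 8.0% against 4/40 = 10.0%. Only the step to 4/45 comes from untested patients. The rest comes from also dropping tested baseline-positive patients, which is a separate choice; a common set for induced and boosted is legitimate.
- **A bias that is always downward.** A post-dose positive with no baseline result could count as first positive after dosing: 5/50 = 10.0% against 4/49 = 8.2% without that patient. The net direction is not established.
- **An invalid infusion-reaction table.** SAP 6.6.1 tabulates these reactions by ADA status. On planned days the last Cycle 1 reaction window closes on Day 8 (Day 12 with delays), and the earliest post-dose ADA sample is Day 14. For Cycle 1 the table is therefore a descriptive association, which calls for a note and not a new analysis.

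**Conclusion.** Both defects are in the SAP text and are worth correcting, but they touch only descriptive secondary summaries. No decision rule uses them, and the primary QTcF conclusion is unchanged.

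The denominator rule dilutes the overall, induced and boosted percentages. It does not distort the baseline percentage, where untested patients belong, or the transient/persistent split, which contains only induced patients. The size rests on assumed counts: 8.0% against 8.2% to 8.9% for 4 positives in 50 and 1 to 5 untested, well within sampling error. A reader might infer that ADA incidence will be materially understated; the documents do not give the untested count and so cannot show that.

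The classification defect does not depend on assumed counts. On the planned schedule every early single positive cleared by EOT falls in both classes, and several positives under 16 weeks apart ending in a positive sample fall in neither. How many patients will show these patterns is unknown. Two cases are not part of the demonstrated overlap: several positives with a negative last sample, which depends on how the persistent condition is read, and a patient positive only at EOT who is negative at first follow-up, where the SAP's exception for later undetectability points to transient.

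**What to change.** **Denominator.** Compute the overall, induced and boosted percentages among patients with at least one post-dose ADA (or NAb) result. Use one common denominator so that induced plus boosted still equals overall. Print the number without a post-dose result and the number without a baseline result. SAP 3.2.2 characterizes NAb only in ADA-positive samples, so state that a negative ADA result counts as a NAb-negative result; otherwise the NAb denominator would shrink to ADA-positive patients.

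**Classes.** Either delete the condition on positives less than 16 weeks before a negative last sample, or add an explicit precedence rule. Deletion makes early single positives cleared by EOT transient; precedence for persistent would leave none of them transient on this schedule. In the same edit, assign the pattern of several positives under 16 weeks apart with a positive last sample. It could be persistent, in line with the existing rule for a positive last sample, or an indeterminate row. Footnote the number of patients affected and apply the same rules to NAb.

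**Optional.** Add a note under the infusion-reaction table that post-dose ADA status is first measured after the Cycle 1 reaction windows close.

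**Cost.** SAP wording and table programming on samples already planned, with no change to visits or procedures. The denominator becomes slightly smaller, and deleting the clause favours the milder class, which is why the footnote is needed.
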